12.3	Sample Size, Accrual Rate and Study Duration	27
12.4	Stratification Factors	28
12.5	Interim Monitoring Plan	28
12.6	Analysis of Primary Endpoints	28
12.7	Analysis of Secondary Endpoints	28
12.8	Reporting and Exclusions	31
13.	REGULATORY CONSIDERATIONS.....	32
13.1	Data Safety Monitoring.....	32
14.	PUBLICATION PLAN	32
	REFERENCES	34
APPENDIX A	PERFORMANCE STATUS CRITERIA	37
APPENDIX B	M. D. Anderson Symptom Inventory – Brain Tumor survey.....	38

SCHEMA

Patients with recurrent glioblastoma, eligible for re-irradiation

Tumor or tumor cavity ≤ 10 cm

KPS ≥ 70

Age ≥ 18

Full recovery after any recent surgery
> 3 months after initial course of radiation therapy

Model-Adapted Radiation fractionation Schedule (MARS)

10 treatment days over 2 weeks

Based upon reference dosing of 35 Gy / 10 fractions

Follow up

Clinic visits and MRI Brain every 1-3 months per standard clinical practice

1. INTRODUCTION

1.1 Study Disease

Glioblastoma is the most common primary malignant brain tumor in adults, occurring at a rate of 3.66 new cases per 100,000 people per year in the United States (1). The role of adjuvant radiation therapy after surgical resection for glioblastoma was established in the 1970s and 1980s through several historic randomized trials comparing radiotherapy to observation (2–4), chemotherapy (3–5), or combination therapy (3–5). These studies largely showed that post-operative radiotherapy increased the median survival from 3.2-6.0 months to 8.0-12.8 months, establishing radiation therapy as a standard component to treatment for glioblastoma.

Modern treatment for glioblastoma has built upon this backbone of post-operative radiotherapy to include concurrent and adjuvant temozolomide chemotherapy, following a landmark study in 2005 showing the addition of chemotherapy to raise median survival from 12.1 months to 14.6 months (6). Despite optimal combined modality therapy with surgery, radiation, and chemotherapy, survival outcomes remain poor with most patients progressing within 10-15 months and surviving only 14.6-16.2 months from their initial diagnosis (7). The prognosis for patients upon first progression is similarly poor, with most patients only surviving approximately 4 months from progression (8,9).

Re-irradiation is a common treatment component for locally recurrent glioblastoma, often in combination with surgery and/or chemotherapy. Based on a large institutional series of 147 patients with recurrent high grade glioma treated with fractionated stereotactic re-irradiation resulting in a median survival of 11 months with excellent treatment tolerance, a standard regimen for re-irradiation is 35 Gy delivered in 10 fractions over two weeks (10). Based on these data the RTOG is actively testing this regimen in a prospective randomized study with and without concurrent bevacizumab therapy for recurrent glioblastoma (11).

The predominant pattern of initial and subsequent failure in glioblastoma is local, with 75-93% of first recurrences occurring within the high-dose volume of radiotherapy (12–18). Accordingly, several prior studies have investigated intensification of local therapy. In the era before modern chemotherapy, such studies showed improved overall survival with conventionally fractionated radiation doses to 60 Gy over 45 Gy (19). However, efforts to dose-escalate further to 70 Gy (20) and 80 Gy (21) did not significantly improve survival or patterns of failure. Similarly, randomized studies investigating intensification of local therapy with stereotactic boosting (22) and brachytherapy (23) showed no improvement in outcomes.

Explanations for this paradoxical risk of local recurrence that is refractory to intensive local therapy have included intratumoral hypoxia, genomic and phenotypic heterogeneity, and limitations of current models of radioresistance. Conventionally “fractionated” radiation schedules are based largely on the linear-quadratic model which is commonly used to estimate the probability of tumor control and normal tissue complications (24). Despite good concordance with experimental results in other cancers (25,26), efforts to optimize radiation schedules based on the linear-quadratic model have not proven effective in the clinical setting for aggressive gliomas (27).

1.2 Rationale

These limitations have drawn interest in re-designing radiation schedules, accounting for mechanisms of treatment resistance. Recent work by Leder, Michor and colleagues has created a novel mathematical model of a major mechanism of treatment resistance by accounting for intratumor heterogeneity. Specifically, they modeled the evolutionary dynamics of radioresistant, slowly proliferating stem-like cells and radiosensitive, rapidly proliferating differentiated cells. They used this model to determine an optimized radiation fractionation schedule. They parametrized the mathematical model and validated the predicted optimal schedules using a genetically engineered mouse model of PDGF-driven proneural glioblastoma (28,29). The investigators refined their mathematical model and its underlying biological assumptions through an iterative process of mathematical modeling and experimental validation. The mathematical model suggested that survival could be prolonged by enriching the tumor for slowly proliferating stem-like cells. The model predicted that the stem-like cell fraction could be substantially increased by timing the radiation administrations such that the radiation-induced dedifferentiation from differentiated to stem-like cells was maximized. When the initial predicted optimal schedule was tested in a mouse model of PDGF-driven glioblastoma, this model-adapted radiation schedule did, as predicted, significantly increase the stem-like cell fraction and significantly improved survival relative to conventionally fractionated radiation among treated mice (median survival 50 days vs. 33 days, HR = 0.30, p=0.001) (29). A second optimal schedule, based on updating the model to account for time-dependent dedifferentiation from differentiated to stem-like cells, resulted in a further, non-significant, improvement in survival compared with the original optimal schedule (HR = 0.88, p = 0.18). The updated mathematical model fit the experimental data better than the original model.

Further evidence from human data suggest that enriching the stem-like cell fraction may represent a suitable strategy to prolong survival in patients. In a study by Pallini and colleagues, the stem-like cell fraction was measured at the time of primary surgery and at recurrence, i.e. before and after chemo-radiation therapy, in glioblastoma patients (30). The stem-like cell enrichment was significantly associated with recurrence-free survival, survival following recurrence and overall survival.

We have used the validated mathematical model to translate the optimal schedule used in the mouse experiments (based on delivering 10 Gy in 5 days) to humans, using the same toxicity constraints and overall treatment time as in the RTOG 1205 trial. The mathematical model predicts that tumor growth delay is increased by enriching the slowly proliferating, stem-like cell population. The model predicts that this is achieved in two ways: by increasing the total radiation dose delivered and by increasing the fraction of differentiated cells that dedifferentiate to stem-like cells. Ultrafractionation (three fractions per day) greatly increases the stem-like cell fraction leading to a slower tumor regrowth following the end of treatment. However, by enriching for stem-like cells early during treatment the number of radioresistant cells increases and, hence, the effectiveness of the remaining fractions of radiation decreases. In addition to enriching the stem-like cell population, survival can be prolonged by minimizing the total number of cells. The total cell number is minimized by increasing the total radiation dose. Through using the model to simulate different treatment strategies, it is apparent that it is

desirable to obtain a balance between minimizing the total cell number and maximizing the stem-like cell fraction at the end of treatment. This can be achieved, within toxicity and practicality constraints, using an initial phase of hypofractionation to deliver a relatively high dose in a short period to reduce the total cell number with a small number of fractions. By following this with an ultrafractionation phase the slowly proliferating stem-like cell population is enriched at the end of treatment resulting in slower tumor regrowth and, hence, prolonged survival. The proposed treatment schedule consists of 3.96 Gy delivered once per day for the first seven treatment days followed by 1.0 Gy delivered three times per day with a 3.25-hour interval between fractions for the final three treatment days.

Indeed, ultrafractionation has been investigated in glioblastoma with promising results relative to historical controls and no reported grade 3-4 acute adverse events (31), emphasizing the promise and safety of this approach.

We hypothesize that this novel, model-based radiation fractionation scheme will be safe and deliverable for patients with recurrent glioblastoma. This study will use the previously derived mathematical model to optimize a commonly used 2-week dose-fractionation scheme for re-irradiation in glioblastoma (2), currently the standard re-irradiation regimen of the Radiation Therapy Oncology Group (11).

2. OBJECTIVES

2.1 Study Design

This is a non-randomized feasibility trial of a novel mathematical model-adapted radiation fractionation schedule, adapted from a standard 2-week treatment regimen for re-irradiation in glioblastoma (10).

2.2 Primary Objective

To assess the feasibility of delivering a mathematical model-adapted radiation schedule over 2-weeks for re-irradiation in recurrent glioblastoma.

2.3 Secondary Objectives

To evaluate patient-reported outcomes and patient satisfaction among participants receiving re-optimized radiation schedules.

To prospectively evaluate acute treatment-related toxicity from this re-optimized re-irradiation regimen.

To prospectively evaluate the following other endpoints among patients receiving this re-optimized re-irradiation regimen:

1. All-cause mortality

2. Incidence and time to local recurrence
3. Incidence and time to development of radiation necrosis
4. Incidence and time to salvage craniotomy
5. Incidence and time to systemic treatments after re-irradiation
6. Incidence and time to the development of seizures

3. PARTICIPANT SELECTION

3.1 Eligibility Criteria

Participants must meet the following criteria to be eligible for the study:

- 3.1.1 Participants must have recurrent glioblastoma (WHO Grade IV), as defined on brain imaging with CT or MRI, after prior receipt of definitive therapy including neurosurgical biopsy or resection and radiation therapy with or without systemic therapy.
- 3.1.2 Participants must be deemed appropriate candidates for re-irradiation
- 3.1.3 Histopathologic confirmation of disease as part of routine clinical care is required either at the time of initial diagnosis and/or at the time of recurrent disease. There is no requirement for central pathologic review.
- 3.1.4 Age \geq 18 years at the time of enrollment
- 3.1.5 Karnofsky Performance Status (KPS) of at least 70

3.2 Exclusion Criteria

- 3.2.1 Participants who have received more than one prior course of radiotherapy to the local site of progressive disease
- 3.2.2 Participants who have received prior radiotherapy to the local site of progressive disease within < 3 months of the anticipated start of re-irradiation
- 3.2.3 Participants with recurrent tumor extensively abutting or involving the optic structures or brainstem, as assessed by the treating radiation oncologist
- 3.2.4 Participants without a definable tumor cavity on MRI or CT obtained at study enrollment
- 3.2.5 Participants receiving concurrent cytotoxic chemotherapy (i.e. temozolomide, CCNU, vincristine, procarbazine) or concurrent immunotherapy (i.e. pembrolizumab, nivolumab); however, participants may receive sequential chemotherapy before or after radiation without limitation. Participants may receive concurrent corticosteroid and/or anti-angiogenic therapy (i.e. bevacizumab) if clinically indicated.

3.3 Inclusion of Women and Minorities

Both men and women of all races and ethnic groups are eligible for this trial.

4. PRETREATMENT EVALUATIONS/MANAGEMENT

Patients presenting to Brigham and Women's Hospital who meet the eligibility criteria above will be identified by a radiation oncologist, medical oncologist, or neurosurgeon and offered participation in the study. All patients must have undergone an MRI of the brain with T1 post-contrast sequences (standard of care) or a CT scan (if MRI is not available due to non-compatible devices). No other pretreatment evaluations are required.

5. REGISTRATION PROCEDURES

5.1 General Guidelines for DF/HCC Institutions

Institutions will register eligible participants in the Clinical Trials Management System (CTMS) OnCore. Registrations must occur prior to the initiation of protocol therapy. Any participant not registered to the protocol before protocol therapy begins will be considered ineligible and registration will be denied.

An investigator will confirm eligibility criteria and a member of the study team will complete the protocol-specific eligibility checklist.

Following registration, participants may begin protocol therapy. Issues that would cause treatment delays should be discussed with the Overall Principal Investigator (PI). If a participant does not receive protocol therapy following registration, the participant's registration on the study must be canceled. Registration cancellations must be made in OnCore as soon as possible.

5.2 Registration Process for DF/HCC Institutions

DF/HCC Standard Operating Procedure for Human Subject Research Titled *Subject Protocol Registration* (SOP #: REGIST-101) must be followed.

6. RADIATION THERAPY

6.1 Dose Specifications:

6.1.1 **Treatment Schedule:** Treatment shall consist of a regimen that is biologically equivalent (in terms of biologically effective dose with an alpha/beta ratio of 2) to 35 Gy delivered in 10 fractions over two weeks. Using the regimen developed by Fogh et al (10) and used by RTOG 1205 (35 Gy in 10 fractions) as a standard (11), this protocol has re-optimized the radiation schedule. Radiation therapy will be delivered in 2 phases over 2 weeks with fractions delivered on Monday through Friday only (with no treatments on Saturday or Sunday). All patients will aim to have their first fraction on Monday of week 1. In phase 1, participants will receive 7 daily fractions of 3.96 Gy per fraction. In phase 2, participants will receive 9 fractions of 1.00 Gy per fraction, 3 fractions per day with 3.25 hour interfraction intervals, over 3 days. This idealized treatment schedule is shown in Table 1 and in Figure 1a. Target homogeneity limits and deviations are listed in Table 2. Should any part of the treatment schedule have an anticipated conflict for clinical or logistical reasons (i.e. scheduled department closure for holiday) in which case treatment will not be administered on a given day over the 2-week course, an alternative treatment schedule will be generated utilizing the prediction model for the missing fraction(s). A separate sensitivity analysis was conducted and predicted for a similar benefit of the novel schedule over standard re-irradiation schedule, irrespective of which day of the week treatment is started, as shown in Figure 1b.

Table 1. Idealized Model-Adapted Radiation Schedule*

Week 1	Monday	Tuesday	Wednesday	Thursday	Friday
Dose	1 x 3.96 Gy	1 x 3.96 Gy	1 x 3.96 Gy	1 x 3.96 Gy	1 x 3.96 Gy
Week 2	Monday	Tuesday	Wednesday	Thursday	Friday
Dose	1 x 3.96 Gy	1 x 3.96 Gy	3 x 1.00 Gy (3.25-hour interval)	3 x 1.00 Gy (3.25-hour interval)	3 x 1.00 Gy (3.25-hour interval)

** Schedule subject to predetermined adaptation due to anticipated conflicts (i.e. holidays, department closures, etc....)*

Figure 1a. Idealized Model-Adapted Radiation Schema

[figure not shown]
[figure not shown]

Figure 1b. Sensitivity Analysis for Tumor Response by Day of Treatment Initiation

6.1.2 Tumor Dose Coverage Objectives: The tumor dose coverage objectives are equivalent, in terms of the percentages of the prescription dose, to those used in RTOG 1205 (11). The tumor Planning Target Volume (PTV) dose coverage objectives, for the total absorbed dose delivered in 10 fractions, employed in the RTOG 1205 trial are shown in Table 2.

Table 2. RTOG 1205 Tumor Dose Coverage Objectives (given as absorbed dose)

Dose Metric	Per Protocol	Variation Acceptable	Deviation Unacceptable
Volume of PTV covered by the prescription dose 35 Gy	≥ 95% of the PTV should receive the prescription dose or higher	≥ 90% of the PTV should receive the prescription dose or higher	< 90% of the PTV should receive the prescription dose or higher
Minimum dose to the PTV (0.03 cc)	≥ 85% of the prescription dose (29.75 Gy)	≥ 80% of the prescription dose (28.00 Gy); minimum doses < 80% of the prescription dose are permissible if they occur at an area of overlap with an organ at risk (OAR)	< 80% of the prescription dose (28.00 Gy); minimum doses < 80% of the prescription dose are unacceptable if they do not occur at an area of overlap with an OAR
Maximum dose to the PTV (0.03 cc)	≤ 120% of the prescription dose (42.00 Gy)	≤ 130% of the prescription dose (45.50 Gy)	> 130% of the prescription dose (45.50 Gy)

For MARS-Glio phase 1 the prescription absorbed dose is 3.96 Gy per fraction, giving a cumulative (over 7 fractions) absorbed dose for phase 1 of $3.96 \times 7 = 27.72$ Gy. The tumor dose coverage objectives for phase 1 are shown in Table 3.

Table 3. MARS-Glio phase 1 tumor dose coverage objectives (given as absorbed dose)

Dose Metric	Per Protocol	Variation Acceptable	Deviation Unacceptable
Volume of PTV covered by the prescription dose 27.72 Gy	≥ 95% of the PTV should receive the prescription dose or higher	≥ 90% of the PTV should receive the prescription dose or higher	< 90% of the PTV should receive the prescription dose or higher
Minimum dose to the PTV (0.03 cc)	≥ 85% of the prescription dose (23.56 Gy)	≥ 80% of the prescription dose (22.18 Gy); minimum doses < 80% of the prescription dose are permissible if they occur at an area of overlap with an organ at risk (OAR)	< 80% of the prescription dose (22.18 Gy); minimum doses < 80% of the prescription dose are unacceptable if they do not occur at an area of overlap with an OAR
Maximum dose to	≤ 120% of the	≤ 130% of the	> 130% of the

the PTV (0.03 cc)	prescription dose (33.26 Gy)	prescription dose (36.04 Gy)	prescription dose (36.04 Gy)
--------------------------	------------------------------	------------------------------	------------------------------

For MARS-Glio phase 2 the prescription absorbed dose is 1.00 Gy per fraction, giving a cumulative (over 9 fractions) absorbed dose for phase 2 of $1.00 \times 9 = 9.00$ Gy. The tumor dose coverage objectives for phase 2 are shown in Table 4.

Table 4. MARS-Glio phase 2 tumor dose coverage objectives (given as absorbed dose)

Dose Metric	Per Protocol	Variation Acceptable	Deviation Unacceptable
Volume of PTV covered by the prescription dose 9.00 Gy	$\geq 95\%$ of the PTV should receive the prescription dose or higher	$\geq 90\%$ of the PTV should receive the prescription dose or higher	$< 90\%$ of the PTV should receive the prescription dose or higher
Minimum dose to the PTV (0.03 cc)	$\geq 85\%$ of the prescription dose (7.65 Gy)	$\geq 80\%$ of the prescription dose (7.20 Gy); minimum doses $< 80\%$ of the prescription dose are permissible if they occur at an area of overlap with an organ at risk (OAR)	$< 80\%$ of the prescription dose (7.20 Gy); minimum doses $< 80\%$ of the prescription dose are unacceptable if they do not occur at an area of overlap with an OAR
Maximum dose to the PTV (0.03 cc)	$\leq 120\%$ of the prescription dose (10.80 Gy)	$\leq 130\%$ of the prescription dose (11.70 Gy)	$> 130\%$ of the prescription dose (11.70 Gy)

For MARS-Glio phases 1 and 2 combined the prescription absorbed dose is $3.96 \times 7 + 1.00 \times 9 = 36.72$ Gy. The tumor dose coverage objectives for phases 1 and 2 combined are shown in Table 5.

Table 5. MARS-Glio phases 1 and 2 combined tumor dose coverage objectives (given as absorbed dose)

Dose Metric	Per Protocol	Variation Acceptable	Deviation Unacceptable
Volume of PTV covered by the prescription dose 36.72 Gy	$\geq 95\%$ of the PTV should receive the prescription dose or higher	$\geq 90\%$ of the PTV should receive the prescription dose or higher	$< 90\%$ of the PTV should receive the prescription dose or higher
Minimum dose to the PTV (0.03 cc)	$\geq 85\%$ of the prescription dose (31.21 Gy)	$\geq 80\%$ of the prescription dose (29.38 Gy);	$< 80\%$ of the prescription dose (29.38 Gy);

		minimum doses < 80% of the prescription dose are permissible if they occur at an area of overlap with an organ at risk (OAR)	minimum doses < 80% of the prescription dose are unacceptable if they do not occur at an area of overlap with an OAR
Maximum dose to the PTV (0.03 cc)	≤ 120% of the prescription dose (44.06 Gy)	≤ 130% of the prescription dose (47.74 Gy)	> 130% of the prescription dose (47.74 Gy)

6.1.3 Normal Tissue Constraints: Participants shall receive prescription doses to the PTV (with the above constraints). All attempts should be made to deliver the PTV dose with the above heterogeneity constraints with adherence to critical structure dose constraints. The normal tissue dose constraints are designed to be equivalent in terms of biologically effective dose (BED), to those used in the RTOG 1205 trial. The BED is defined as:

$$BED_{\alpha/\beta} = nd \left(1 + \frac{d}{\alpha/\beta} \right)$$

where n is the number of fractions and d is the dose per fraction. For central nervous system toxicity an alpha/beta ratio of 2 was used. The MARS-Glio dose constraints for the two phases combined in BED with an alpha/beta ratio of 2 are thus given by

$$C_{MARS-Glio,total,BED} = C_{RTOG\ 1205,AD} \left(1 + \frac{C_{RTOG\ 1205,AD}/10}{2} \right)$$

where $C_{RTOG\ 1205,AD}$ is the RTOG 1205 absorbed dose. For the individual phases the dose constraints, in absorbed doses, are given by

$$C_{MARS-Glio,phase\ x,AD} = n_{phase\ x} \left(-1 + \sqrt{1 + \frac{4C_{MARS-Glio,total,BED} \frac{BED_{\alpha/\beta,phase\ x}}{BED_{\alpha/\beta,total}}}{n_{phase\ x} \alpha/\beta}} \right) / 2 / \alpha/\beta$$

$$BED_{2,phase\ 1} = 7 \times 3.96 \left(1 + \frac{3.96}{2} \right) = 82.61\ Gy_2$$

$$BED_{2,phase\ 2} = 9 \times 1.00 \left(1 + \frac{1.00}{2} \right) = 13.50\ Gy_2$$

$$BED_{2,total} = BED_{2,phase\ 1} + BED_{2,phase\ 2} = 96.11\ Gy_2$$

$$\frac{BED_{2,phase\ 1}}{BED_{2,total}} = \frac{82.61}{96.11} = 0.861$$

$$\frac{BED_{2,phase\ 2}}{BED_{2,total}} = \frac{13.50}{96.11} = 0.140$$

$$C_{MARS-Glio,phase\ 1,AD} = 7 \left(-1 + \sqrt{1 + \frac{4C_{MARS-Glio,total,BED} \times 0.861}{7 \times 2}} \right)$$

$$C_{MARS-Glio,phase 2,AD} = 9 \left(-1 + \sqrt{1 + \frac{4C_{MARS-Glio,total,BED} \times 0.140}{9 \times 2}} \right)$$

The dose constraints for the RTOG 1205 trial, in absorbed dose, are displayed in Table 6.

Table 6. RTOG 1205 Normal Tissue Dose Constraints (given as absorbed dose)

Dose Metric	Per Protocol	Variation Acceptable	Deviation Unacceptable
Scenario (1): Previous radiation to the local area including critical organs at risk			
Maximum Dose to PRV for Optic Nerves and Chiasm (D _{0.03 cc})	Less than or equal to 20.00 Gy	Greater than 20.00 Gy but less than or equal to 25.00 Gy	Greater than 25.00 Gy
Maximum Dose to Brainstem (0.03 cc)	Less than or equal to 24.00 Gy	Greater than 24.00 Gy but less than or equal to 30.00 Gy	Greater than 30.00 Gy
Scenario (2): No previous radiation to the local area or critical organs at risk			
Maximum Dose to PRV for Optic Nerves and Chiasm (0.03 cc)	Less than or equal to 35.00 Gy (the prescription dose)	Greater than 35.00 Gy but less than or equal to 36.75 Gy (105 % of the prescription dose)	Greater than 36.75 Gy (105% of the prescription dose)
Maximum Dose to Brainstem (0.03 cc)	Less than or equal to 35.00 Gy (the prescription dose)	Greater than 35.00 Gy but less than or equal to 36.75 Gy (105 % of the prescription dose)	Greater than 36.75 Gy (105 % of the prescription dose)

Table 7 shows the dose constraints for the combined phases in BED with an alpha/beta ratio of 2 for the optic nerves, optic chiasm and brainstem (BED₂).

Table 7. MARS-Glio phases 1 and 2 combined normal tissue dose constraints (given as BED with an alpha/beta ratio of 2)

Dose Metric	Per Protocol	Variation Acceptable	Deviation Unacceptable
Scenario (1): Previous radiation to the local area including critical organs at risk			
Maximum Dose to PRV for Optic Nerves and Chiasm (D _{0.03 cc})	Less than or equal to 40.00 Gy ₂	Greater than 40.00 Gy ₂ but less than or equal to 56.25 Gy ₂	Greater than 56.25 Gy ₂
Maximum Dose to Brainstem (0.03 cc)	Less than or equal to 52.80	Greater than 52.80 Gy ₂ but less than or equal	Greater than 75.00 Gy ₂

	Gy ₂	to 75.00 Gy ₂	
Scenario (2): No previous radiation to the local area or critical organs at risk			
Maximum Dose to PRV for Optic Nerves and Chiasm (0.03 cc)	Less than or equal to 96.11 Gy ₂ (the prescription dose)	Greater than 96.11 Gy ₂ but less than or equal to 104.28 Gy ₂	Greater than 104.28 Gy ₂
Maximum Dose to Brainstem (0.03 cc)	Less than or equal to 96.11 Gy ₂ (the prescription dose)	Greater than 96.11 Gy ₂ but less than or equal to 104.28 Gy ₂	Greater than 104.28 Gy ₂

Tables 8 and 9 give the phase 1 and phase 2 normal tissue dose constraints in absorbed doses, respectively.

Table 8. MARS-Glio phase 1 normal tissue dose constraints (given as absorbed dose)

Dose Metric	Per Protocol	Variation Acceptable	Deviation Unacceptable
Scenario (1): Previous radiation to the local area including critical organs at risk			
Maximum Dose to PRV for Optic Nerves and Chiasm (D _{0.03 cc})	Less than or equal to 16.05 Gy	Greater than 16.05 Gy but less than or equal to 19.96 Gy	Greater than 19.96 Gy
Maximum Dose to Brainstem (0.03 cc)	Less than or equal to 19.18 Gy	Greater than 19.18 Gy but less than or equal to 23.87 Gy	Greater than 23.87 Gy
Scenario (2): No previous radiation to the local area or critical organs at risk			
Maximum Dose to PRV for Optic Nerves and Chiasm (0.03 cc)	Less than or equal to 27.75 Gy	Greater than 27.75 Gy but less than or equal to 29.14 Gy	Greater than 29.14 Gy
Maximum Dose to Brainstem (0.03 cc)	Less than or equal to 27.75 Gy	Greater than 27.75 Gy but less than or equal to 29.14 Gy	Greater than 29.14 Gy

Table 9. MARS-Glio phase 2 normal tissue dose constraints (given as absorbed dose)

Dose Metric	Per Protocol	Variation Acceptable	Deviation Unacceptable
Scenario (1): Previous radiation to the local area including critical organs at risk			
Maximum Dose to	Less than or	Greater than 4.48 Gy	Greater than 5.93

PRV for Optic Nerves and Chiasm (D _{0.03 cc})	equal to 4.48 Gy	but less than or equal to 5.93 Gy	Gy
Maximum Dose to Brainstem (0.03 cc)	Less than or equal to 5.63 Gy	Greater than 5.63 Gy but less than or equal to 7.43 Gy	Greater than 7.43 Gy
Scenario (2): No previous radiation to the local area or critical organs at risk			
Maximum Dose to PRV for Optic Nerves and Chiasm (0.03 cc)	Less than or equal to 8.98 Gy	Greater than 8.98 Gy but less than or equal to 9.54 Gy	Greater than 9.54 Gy
Maximum Dose to Brainstem (0.03 cc)	Less than or equal to 8.98 Gy	Greater than 8.98 Gy but less than or equal to 9.54 Gy	Greater than 9.54 Gy

See Section 6.5 below for specifics regarding when to implement a dose reduction. The final prescription dose will be reported specifically to the study coordinator and recorded on a patient-by-patient basis.

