6.5 Critical Structures

Critical structure dose constraints shall remain consistent with Tables 7-9 above. While every effort should be made to deliver prescription doses to the PTV as specified while adhering to these constraints, it is recognized that certain anatomical factors may prevent this.

For purposes of compliance, up to a 5% absolute increase in the volume of critical structure receiving greater than the specified dose will be considered “variation acceptable,” without a protocol deviation. Any increase in critical structure volume greater than 5% receiving more than the specified dose will be considered a “deviation unacceptable.” It is at this point that a dose reduction should be considered.

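### Section 6.1.3 uses a phase 1 BED share of 0.861 where the ratio is 0.8595, so the Table 8 limits are 0.02–0.03 Gy too high and Tables 8 and 9 do not quite agree with Table 7

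*Combined protocol and SAP*

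**What the plan says.** Under Section 6.1.1, in phase 1 "participants will receive 7 daily fractions of 3.96 Gy per fraction", and in phase 2 "participants will receive 9 fractions of 1.00 Gy per fraction". Section 6.1.3 sets normal-tissue limits meant to match those of RTOG 1205 in BED with an alpha/beta ratio of 2. Table 7 gives the limits for both phases combined. Each is then split into phase limits in absorbed dose according to the phase's share of the total BED.

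The phase 1 share is printed as "82.61}{96.11} = 0.861", the phase 2 share as 0.140, and both are carried into the phase formulas. The results are Table 8 (phase 1; the first entry is "Less than or equal to 16.05 Gy") and Table 9 (phase 2; the scenario 2 middle category is "Greater than 8.98 Gy but less than or equal to 9.54 Gy").

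For scenario 2, the Table 7 per-protocol limit is "Less than or equal to 96.11 Gy" (in BED units), labelled as the prescription dose. Table 4 in Section 6.1.2 gives the phase 2 prescription: "Volume of PTV covered by the prescription dose 9.00 Gy". Section 6.5 keeps all three constraint tables in force: "Critical structure dose constraints shall remain consistent with Tables 7-9 above".

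**The concern.** The two shares divide one total, so they must sum to 1. As printed they sum to 1.001, and 82.61/96.11 is not 0.861. Correct rounding to three decimals would give 0.860.

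These shares generate the cut-points that class a plan as per protocol, acceptable variation or unacceptable deviation for the optic structures and brainstem. If 0.861 was used and not merely misprinted, Table 8 is slightly permissive and the phase limits do not add back to the combined limits. A plan could then meet Tables 8 and 9 and fail Table 7, or meet Tables 7 and 8 and fall into a lower class in Table 9.

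**Working it through.** **Inputs.** Phase 1: n = 7, d = 3.96 Gy. Phase 2: n = 9, d = 1.00 Gy (Section 6.1.1). Alpha/beta = 2 (Section 6.1.3). Combined limits C from Table 7: 40.00, 56.25, 52.80, 75.00, 96.11 and 104.28 Gy2.

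**Shares.** BED = n·d·(1 + d/2).

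- Phase 1: 7 × 3.96 × 2.98 = 82.6056
- Phase 2: 9 × 1.00 × 1.5 = 13.50
- Total: 96.1056
- Phase 1 share: 82.6056/96.1056 = 0.85953 (the rounded inputs 82.61/96.11 give 0.85954)
- Phase 2 share: 13.50/96.1056 = 0.14047
- Printed shares: 0.861 + 0.140 = 1.001

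**Phase limits.** With alpha/beta = 2, the formula with numbers inserted is: limit = n·(−1 + √(1 + 2·C·share/n)).

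Phase 1 (Gy):

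| C (Gy2) | Table 8 | share 0.861 | unrounded share |
|---|---|---|---|
| 40.00 | 16.05 | 16.047 | 16.029 |
| 56.25 | 19.96 | 19.964 | 19.942 |
| 52.80 | 19.18 | 19.181 | 19.160 |
| 75.00 | 23.87 | 23.872 | 23.847 |
| 96.11 | 27.75 | 27.749 | 27.721 |
| 104.28 | 29.14 | 29.138 | 29.109 |

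The share 0.861 returns every Table 8 value, so it was used in the calculation. A share of 0.860 does not (it gives 16.035 and 29.118 in the first and last rows). The cell 27.75 is not proof by itself, because C = 96.25 with the unrounded share also gives it (27.745). The other five cells have no such alternative, since their Table 7 limits follow the stated formula.

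Phase 2 (Gy):

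| C (Gy2) | Table 9 | share 0.140 | unrounded share |
|---|---|---|---|
| 40.00 | 4.48 | 4.483 | 4.496 |
| 56.25 | 5.93 | 5.925 | 5.941 |
| 52.80 | 5.63 | 5.631 | 5.646 |
| 75.00 | 7.43 | 7.432 | 7.451 |
| 96.11 | 8.98 | 8.978 | 9.000 |
| 104.28 | 9.54 | 9.541 | 9.565 |

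The cell 5.93 follows neither share: 0.140 gives 5.9248, which rounds to 5.92, and the unrounded share gives 5.94.

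**Recombining the printed limits.** BED of a phase limit x is x·(1 + x/(2n)). First row: 16.05 × (1 + 16.05/14) = 34.45 and 4.48 × (1 + 4.48/18) = 5.595, total 40.05.

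| Table 7 (Gy2) | Tables 8 + 9 (Gy2) | excess | excess with each printed limit lowered by 0.005 Gy |
|---|---|---|---|
| 40.00 | 40.05 | 0.05 | 0.021 |
| 56.25 | 56.30 | 0.05 | 0.023 |
| 52.80 | 52.85 | 0.05 | 0.021 |
| 75.00 | 75.07 | 0.07 | 0.034 |
| 96.11 | 96.21 | 0.10 | 0.070 |
| 104.28 | 104.39 | 0.11 | 0.073 |

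The last column shows that two-decimal display does not account for the excess.

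**The 96.11 entry.** The stated conversion at 35.00 Gy gives 35 × (1 + 3.5/2) = 96.25, not 96.11. The printed 96.11 equals this trial's own prescription BED (96.1056) and carries that label, so it looks like a deliberate, slightly stricter choice, but the text does not say that it replaces the formula value. Against 96.25, the fifth row (96.21) would show no excess. The other five rows do not depend on this.

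**Scenario 2 at prescription.** An organ maximum of 27.72 Gy in phase 1 and 9.00 Gy in phase 2 has a BED of 96.11 Gy2. That is per protocol in Table 7 and in Table 8 (27.72 ≤ 27.75), but an acceptable variation in Table 9 (9.00 > 8.98). Unrounded shares return limits of 27.72 and 9.00 Gy.

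**The case against.** The case against giving this weight is mostly about consequence, and much of it stands.

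- **Size.** The differences are hundredths of a gray per phase and about 0.1% in combined BED. The primary endpoint is receipt of fractions on schedule, so no sample size, analysis or decision rule depends on these limits. This stands.
- **The strictest table governs.** If all three tables apply, a plan at both phase limits must still meet Table 7, so the slip does not license a higher combined dose. That is a fair reading, but Section 6.5 does not state it. It also leaves the Table 9 limit below prescription in scenario 2.
- **The scenario 2 example triggers nothing.** Section 6.5 ties consideration of a dose reduction to an unacceptable deviation, not to an acceptable variation. Scenario 2 should also be uncommon, since all participants have had radiotherapy and tumors extensively abutting or involving the optic structures or brainstem are excluded. This stands, although the unacceptable-deviation cut-points in Table 8 carry the same error.
- **Separate issues.** The phase 2 share of 0.140 is correctly rounded and errs on the strict side, 5.93 is an isolated 0.01 Gy difference, and 96.11 is probably intended. These are fair distinctions: the error proper is 0.861, and the rest is tidying best done when the tables are re-derived.
- **Residual rounding.** Corrected limits rounded to two decimals still exceed Table 7 in four of six rows, by 0.005–0.016 Gy2. True; rounding down removes it.

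None of this makes 0.861 the right quotient.

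**Conclusion.** The concern holds as a minor arithmetic error. The phase 1 share is 0.8595, the protocol used 0.861, and the Table 8 limits are 0.02–0.03 Gy too high as a result. Tables 8 and 9 together exceed Table 7 as printed at all six distinct limits, by 0.05–0.11 Gy2; at five of them this holds whichever value is intended for the 96.11 entry. The result rests only on the protocol's own formulas and fractionation.

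An organ maximum must sit almost exactly at a limit for a plan to change class, so few plans would be affected, and no clinical effect is to be expected. It is worth correcting because these are operative cut-points for re-irradiated critical structures and the inconsistency is visible on the page.

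**What to change.** Replace the shares with unrounded values (0.8595 and 0.1405 as displayed, summing to 1) and re-derive Tables 8 and 9. With Table 7 as printed:

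| Table 7 (Gy2) | Phase 1 (Gy) | Phase 2 (Gy) |
|---|---|---|
| 40.00 | 16.03 | 4.50 |
| 56.25 | 19.94 | 5.94 |
| 52.80 | 19.16 | 5.65 |
| 75.00 | 23.85 | 7.45 |
| 96.11 | 27.72 | 9.00 |
| 104.28 | 29.11 | 9.57 |

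These pairs recombine to within 0.02 Gy2 of Table 7. If meeting Tables 8 and 9 is to guarantee Table 7, round the unrounded limits down instead of to the nearest 0.01 Gy.

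Add one sentence saying that 96.11 Gy2 is this trial's prescription BED, used in place of the formula's 96.25. Alternatively, change the entry to 96.25, in which case the phase limits are 27.75 and 9.01 Gy.

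The cost is a table correction and one sentence, which can go into an amendment.
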